4.5.3 Cases and controls identification

Depending on the data source used: IPD surveillance (laboratory based or hospital based), or hospital discharge data bases, the identification includes:

- Admission for compatible clinical syndromes or discharge with a compatible diagnostics code (Table 2. ICD codes)
- Link with or data provided by laboratories (including serotypes)
- ► Each surveillance site to describe how the case identification is done according to data sources. In any case, the individual data collection will require a link between the clinical, laboratory and vaccination data.

4.5.4 Cases and controls inclusion and exclusion criteria

IPD/SpCAP cases and controls will be included if individuals are eligible for PCV13 or PPSV23 vaccination, were hospitalised for an IPD or SpCAP, and have had the serotype identified.

IPD cases and controls will be excluded if:

-

²³ Andrews, N., et al. Impact and effectiveness of 23-valent pneumococcal polysaccharide vaccine against invasive pneumococcal disease in the elderly in England and Wales. Vaccine 2012: 30, 6802–6808

- Individuals are not eligible for vaccination due to conditions that contra-indicate vaccination;
- Testing of non-sterile body fluid was used for diagnosis;
- Recurrent invasive disease is diagnosed (only the first episode will be included in the analysis). Recurrent invasive disease is defined as IPD episodes in the same individual with the diagnosis/admission date at 30 days apart or identification of the same serotype.
- Serotyping could not be performed.

SpCAP cases and controls will be excluded if:

- Individuals are not eligible for vaccination due to conditions that contra-indicate vaccination;
- Recurrent disease is diagnosed (only the first episode will be included in the analysis). Recurrent
 disease is defined as SpCAP episodes in the same individual with the diagnosis/admission date at 30
 days apart or identification of the same serotype.
- Serotyping could not be performed.

4.5.5 Laboratory methods

To comply with the IPD case definition, laboratory confirmation through culture, PCR or antigen detection could be used for diagnosis in order to allow serotyping. Serotyping is of paramount importance as it is required for IPD cases inclusion and it makes the differentiation between cases and controls.

- Isolation and identification/ PCR could be done at the hospital laboratory or at the reference laboratory
- Serotyping of isolates is usually done at the reference laboratory using capsular reaction testing (Quellung test), PCR or gel diffusion with type-specific antisera
- Antimicrobial susceptibility testing should be done for all isolates for at least the following antimicrobials: penicillin, macrolide, and cephalosporin. MIC will be reported and EUCAST clinical breakpoints used will be used for classification

Specimen collection, transportation and tests used are well defined in case an IPD surveillance system is in place.

For non-invasive SpCAP, the diagnosis can be made using similar tests from non-sterile fluids (sputum, tracheobronchial aspirates, urine, etc.) or the urine antigen testing which allows serotyping.

▶ Each study site to describe how specimens are collected, transported and types of the tests performed for confirmation and serotyping. When confirmation and serotyping was done by PCR, the method and the algorithms used should be described. The sensitivity and specificity of all tests should be provided.

4.6 Exposure

4.6.1 Definition of vaccination status

- Unvaccinated: absence of records of vaccination with PCV13 or PPSV23 in the vaccination registry or medical records, or if the vaccine dose was given less than 14 days prior to onset of symptoms;
- Vaccinated with PCV13: individuals that have received at least one dose PCV13 at least 14 days before onset of symptoms;
- Vaccinated with PPSV23: individuals who have received at least one dose of PPSV23 at least 14 days before onset of symptoms regardless the age and time since vaccination;

TECHNICAL DOCUMENT – Protocol on effectiveness of Pneumo vaccines in elderly

- Vaccinated with both PCV13 and PPSV23: individuals who have received both vaccines, the last one received at least 14 days before onset of symptoms, regardless the age and time since vaccination with the first provided vaccine;
- Repeated vaccination with PPV23: individuals who received more than one dose of PPV23, the
 last one at least 14 days before onset of symptoms regardless the age and time since
 vaccination;
- Uncertain vaccination history: individuals with no vaccination information available (no written
 medical records or no registry available, brand name not mentioned, date of administration
 unknown) or vaccinated during a clinical trial.

4.6.2 Vaccination status ascertainment

The exposure of interest in this study is the history of vaccination with any of PPSV23 or PCV13 vaccines. The vaccination history includes number of doses, date of administration of each dose and brand of each vaccine.

Vaccination status is extracted from available data sources: vaccination registry, hospital or family physicians medical records, or vaccination cards. Efforts should be made to validate the vaccination status. Information on individuals with no information on vaccination status is collected and considered for the sensitivity analysis.

► Each study site to describe the quality and source of the vaccination data and whether they plan to validate the vaccination ascertainment using other sources or studies (vaccination survey, etc.).

4.7 Confounding factors and effect modifiers

Individual data collection is required for all IPD cases for surveillance purposes. A minimum set of variables to be collected in the enhanced surveillance systems are included in the table 3. Efforts should be made to harmonise the data collected by all sites.

To control for differences in the characteristics of VT-IPD cases and NVT-IPD controls, information on potential confounding factors should be collected. Those factors will include:

- Age;
- Gender;
- Time of diagnosis (year or month);
- Underlying conditions and other risk factors included in the recommendation for pneumococcal vaccination as defined Table 3 (end of the document). A minimum set of data on high risk conditions will be collected. The sites can include additional data if available;
- Functional status (Barthel index or other criteria available in the site);
- Influenza vaccination in the current season.

Other confounding factors can be included in addition to those already collected for IPD surveillance: number of children in the family, indicators of socio-economic status, smoking history etc.

► Each study site to define the variables used to identify potential confounding factors or effect modifiers and source of identification if different than data collected for surveillance purposes.

4.8 Power and sample size and calculation

a) Power calculation

According to the number of cases and controls (i.e. VT-IPD cases and NVT-IPD controls, respectively) collected in the IPD surveillance system, we can calculate the power to detect a given vaccine effectiveness (i.e. 1-odds ratio for vaccination). In order to calculate the power, the following parameters should be taken into account:

- the vaccination coverage in the site;
- number of cases, i.e. VT-IPD;
- number of controls, i.e. NVT-IPD;
- predicted vaccine effectiveness depending on the outcome and exposure;
- a significance level of 5%.

For example, in case of o sample size of 100 VT-IPD cases and 300 NVT-IPD controls, the power will vary according to the vaccination coverage and predicted vaccination effectiveness (Figure 1)

[figure not shown]

Figure 1. Power calculation for different vaccination coverage (VC), vaccine effectiveness, for a sample size of 100 VT-IPD and 300 NVT-IPD

b) Sample size calculation

In case not sufficient number of IPD cases are collected by the surveillance system in a given period of time, the sample size should be calculated in order to reach the desired power and precision of VE estimate. To calculate the sample size, the following parameters should be taken into account:

- a significance level of 5%;
- a power of 80%;
- a precision of 20% around the point VE estimate;
- the vaccination coverage available in the site;
- a vaccine effectiveness of 20%-90% depending on the outcome and exposure;
- a proportion of PPV23-IPD among the all IPD cases of 0.60 (based on SpIDnet1 data in >64 years 2012-2014).

The calculation should be done according to each outcome considered: primary outcome (IPD of vaccine serotypes) and secondary outcomes (specific vaccine serotypes/vaccine related serotypes, clinical manifestation, IPD antimicrobial non-susceptibility and severe IPD of vaccine serotypes).

Table 4 presents the sample size needed to reach the chosen precision around point estimate.

Table 4. Sample size needed for the for different vaccine coverages and vaccine effectiveness.

Precision	Alpha	Power	Proportion of vaccine type/ all cases	Vaccine coverage in the source population	Detectable VE(1-OR)	Number of cases	Number of controls	Total IPD patients included
0.2	0.05	0.8	0.6	0.1	0.9	346	231	576
0.2	0.05	8.0	0.6	0.1	0.8	509	339	849
0.2	0.05	8.0	0.6	0.1	0.7	717	478	1195
0.2	0.05	8.0	0.6	0.1	0.6	963	642	1605
0.2	0.05	8.0	0.6	0.1	0.5	1246	831	2077
0.2	0.05	8.0	0.6	0.1	0.4	1566	1044	2610
0.2	0.05	8.0	0.6	0.1	0.3	1922	1281	3203
0.2	0.05	8.0	0.6	0.1	0.2	2315	1543	3858
0.2	0.05	8.0	0.6	0.3	0.9	104	69	173
0.2	0.05	8.0	0.6	0.3	0.8	167	111	278
0.2	0.05	8.0	0.6	0.3	0.7	251	167	418
0.2	0.05	0.8	0.6	0.3	0.6	354	236	590
0.2	0.05	8.0	0.6	0.3	0.5	476	317	793
0.2	0.05	8.0	0.6	0.3	0.4	617	411	1028
0.2	0.05	0.8	0.6	0.3	0.3	777	518	1295
0.2	0.05	8.0	0.6	0.3	0.2	957	638	1595
0.2	0.05	8.0	0.6	0.5	0.9	58	38	96
0.2	0.05	8.0	0.6	0.5	0.8	106	70	176
0.2	0.05	8.0	0.6	0.5	0.7	171	114	285
0.2	0.05	8.0	0.6	0.5	0.6	255	170	424
0.2	0.05	8.0	0.6	0.5	0.5	356	238	594
0.2	0.05	8.0	0.6	0.5	0.4	477	318	794
0.2	0.05	8.0	0.6	0.5	0.3	616	411	1027
0.2	0.05	8.0	0.6	0.5	0.2	891	594	1484
0.2	0.05	8.0	0.6	0.7	0.9	43	29	72
0.2	0.05	8.0	0.6	0.7	0.8	94	63	157
0.2	0.05	8.0	0.6	0.7	0.7	166	111	277
0.2	0.05	8.0	0.6	0.7	0.6	260	174	434
0.2	0.05	8.0	0.6	0.7	0.5	379	253	631
0.2	0.05	8.0	0.6	0.7	0.4	523	348	871
0.2	0.05	8.0	0.6	0.7	0.3	693	462	1154
0.2	0.05	8.0	0.6	0.7	0.2	891	594	1484

[▶] Each study site to estimate the power and/or calculate the sample size according to the available parameters.

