5.3 Measure of association

Vaccine effectiveness will be computed as 100% X (1 – the odds of vaccination in VT cases / odds of vaccination in NVT controls). An exact 95% confidence interval will be computed around the point estimate. The crude and adjusted estimates of vaccine effectiveness will be provided.

The VE will be computed for all exposures mentioned above.

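### Table 4 of section 4.8 b) prints 80% power on every row, but its sizes come from a precision-only formula, so the VE 20% rows deliver only about 50% to 56% power

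*Protocol*

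**What the plan says.** Section 4.8 b) of the protocol sets a joint aim: "the sample size should be calculated in order to reach the desired power and precision of VE estimate". Among its inputs, alpha is 5% and power is 80%. The width target is given as "a precision of 20% around the point VE estimate". Coverage is left for each site to supply. For the assumed effect, the section allows "a vaccine effectiveness of 20%-90% depending on the outcome and exposure". Vaccine-type disease is taken to make up 0.60 of all IPD.

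The sample-size Table 4 in that section has 32 rows (coverage 0.1, 0.3, 0.5 and 0.7, each with VE from 0.9 down to 0.2). Every row carries Precision 0.2, Alpha 0.05, Power 0.8 and a VE in a column headed as detectable. The sentence that introduces the table is narrower: "Table 4 presents the sample size needed to reach the chosen precision around point estimate". The section ends by asking each site to estimate its power, calculate its sample size, or both, from its own parameters.

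**The concern.** A size that guarantees a given precision and a size that guarantees a given power are different quantities, and they agree only by chance. A table showing both as constants across VE values from 20% to 90% therefore needs checking: if one quantity fixed the sizes, the other must vary from row to row.

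This matters because the protocol is a template for sites to adapt, and Table 4 is its only worked sample-size reference. A site or reader consulting a VE 20% row would take it to offer an 80% chance of showing an effect of that size. VE 20% lies inside the range that the protocol itself sets, and the section asks for a calculation for every secondary outcome as well as the primary one.

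**Working it through.** **Inputs.** All come from section 4.8 b): coverage *p0*; OR = 1 − VE; a 60:40 split, so controls are 2/3 of cases; precision 0.20; alpha 0.05. The section does not state sidedness. I take two-sided (z = 1.96), in line with section 5.3 ("An exact 95% confidence interval will be computed around the point estimate"); this value also reproduces the table. The calculation is unadjusted and unmatched.

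**Step 1: reproduce the table.** Vaccinated proportion among cases: *p1* = OR·p0 / (1 − p0 + OR·p0). Variance of the log OR, multiplied by the number of cases: V = 1/[p1(1 − p1)] + 1.5/[p0(1 − p0)]. Set the upper 95% limit of the OR at OR + 0.2, which puts the lower limit of VE 0.20 below the estimate:

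cases = V × [1.96 / ln(1 + 0.2/OR)]²

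At VE 20%, OR = 0.8 and ln(1.25) = 0.2231, so the multiplier is (1.96/0.2231)² ≈ 77.15.

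| Coverage | p1 | V | Cases by formula | Cases printed |
|---|---|---|---|---|
| 0.1 | 0.082 | 30.006 | 2315.0 | 2315 |
| 0.3 | 0.255 | 12.402 | 956.9 | 957 |
| 0.5 | 0.444 | 10.050 | 775.4 | 891 |
| 0.7 | 0.651 | 11.545 | 890.7 | 891 |

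Over all 32 rows the formula returns the printed number of cases, to rounding, in 31. The exception is coverage 0.5 with VE 0.2, whose 891 / 594 / 1484 is identical to the coverage 0.7 entry. The formula gives 775 cases, 775 × 2/3 = 517 controls, and 775.4/0.6 = 1,292 in total.

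None of the power-based formulas tried reproduces the table. At coverage 0.1 and VE 0.2, adding the 80% power term to the same formula gives 4,730 cases against the printed 2,315.

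**Step 2: power at the printed sizes.** With SE from the printed numbers, power = Φ(−ln(OR)/SE − 1.96).

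| VE | Power, two-sided 5% |
|---|---|
| 0.2 | 50% at coverage 0.1, 0.3 and 0.7; 56% at coverage 0.5 as printed (50% at 775 / 517) |
| 0.3 | 79% |
| 0.4 | 94% |
| 0.5 to 0.9 | 98% or more |

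A two-proportion test gives the same picture: 50.1% at VE 0.2 (55.7% at coverage 0.5 as printed), 79% to 80% at VE 0.3, and 93% to 94% at VE 0.4.

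**Step 3: why the VE 20% rows give 50%.** With OR = 0.8 and precision 0.2, OR + 0.2 = 1.0, so the rule places the confidence limit exactly on the null value. The expected z is 1.96, equal to the critical value, and power is Φ(0) = 50% at any coverage. Sidedness does not rescue the figure: a one-sided 5% test gives Φ(1.96 − 1.645) = 62%.

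**Step 4: size for 80% power at VE 20%.** Cases = V × [(1.96 + 0.8416)/0.2231]² ≈ V × 157.6; total = cases / 0.6.

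| Coverage | Total for 80% power | Total printed | Ratio |
|---|---|---|---|
| 0.1 | 7,883 | 3,858 | 2.0 |
| 0.3 | 3,258 | 1,595 | 2.0 |
| 0.5 | 2,640 | 1,484 | 1.8 |
| 0.7 | 3,033 | 1,484 | 2.0 |

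**The case against.** The strongest reply is that the introductory sentence already describes Table 4 as a precision table and that, apart from the repeated row, it delivers the precision it announces. That is true, and it confines the fault to labelling. It does not remove the fault: the same subsection lists 80% power as an input and promises power together with precision, the table prints Power 0.8 on every row and calls the VE detectable, and nothing says that power was not used.

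A second reply is that VE 20% is the edge of the range. The figures the protocol cites for vaccine-type disease are higher: 75% (IPD) and about 45% (CAP) for PCV13, and an average of 60% (range 40% to 70%) for PPSV23 against IPD. This limits the practical reach, especially for the primary outcome. The four rows are nevertheless printed, and a secondary outcome could fall there.

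Two stronger readings are tempting, and the documents support neither:

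- A reader might infer that sites are instructed to size their studies from this table. They are not. Section 4.8 asks each site to do its own calculation, and part a) gives a separate power route from the site's own cases, controls, coverage and expected VE. A site following it would see the low power at VE 20%.
- A reader might infer that sites expecting VE of 50% or more would wrongly judge their data insufficient, because far fewer patients give 80% power. At coverage 0.5 and VE 0.5, for example, 286 would do against 594 printed. But the section asks for 20% precision as well, and the printed number is what that precision requires. A site with half of it does fall short of the protocol's own joint target.

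**Conclusion.** The point holds as a false power statement of limited reach. The constant 0.8 in the Power column is not a property of the sizes beside it. As a minimum it is met in the 24 rows with VE 40% or more and met to within about one percentage point in the four VE 30% rows. It fails clearly in the four VE 20% rows, where meeting it would take about twice the printed total (1.8 times at coverage 0.5 as printed). The coverage 0.5 / VE 0.2 row is also wrong by the table's own rule.

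The estimator, its confidence interval and the analysis in sections 5.3 to 5.5 are unaffected. The figures assume a two-sided 5% test, the 60:40 split, and no matching or covariate adjustment.

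**What to change.** In section 4.8 b):

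1. Remove 80% power as an input to Table 4, or replace the constant Power column with the power each row delivers at two-sided 5%: about 50% at VE 0.2, 79% at 0.3, 94% at 0.4, and 98% or more from 0.5.
2. Correct the coverage 0.5 / VE 0.2 row to about 775 cases, 517 controls and 1,292 in total, so that the 50% applies to it too.
3. Rename the Detectable VE column as Assumed VE.
4. Define precision as the distance from the VE to its lower 95% limit.
5. State that a site wanting both 80% power and 20% precision should take the larger of the two sizes. At VE 20% that is the power-based total in step 4 of the working.

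The cost is wording, one column and one row. The stated power in the VE 20% rows becomes less favourable. No enrolment change is required, since the protocol fixes no enrolment target; a site that chooses to aim for 80% power at VE 20% would need the larger numbers.

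### The sample-size row for coverage 0.5 and VE 0.2 in Table 4 (section 4.8) duplicates the coverage 0.7 row and does not fit the rest of the table; 775/517/1,292 would be consistent with the stated precision

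*Protocol*

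**What the plan says.** Protocol section 4.8 b) lists the inputs for the sample size: a 5% significance level, 80% power, "a precision of 20% around the point VE estimate", the site's vaccination coverage, a VE between 20% and 90%, and "a proportion of PPV23-IPD among the all IPD cases of 0.60". It then introduces the grid: "Table 4 presents the sample size needed to reach the chosen precision around point estimate". (The protocol also has a later Table 4 of ICD codes; the one meant here is the sample-size table.)

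The grid has 32 rows: four coverages (0.1, 0.3, 0.5, 0.7) by eight values of VE (0.9 down to 0.2). Reading coverage, VE, cases, controls and total, the two rows at issue are:

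- coverage 0.5: "0.5 0.2 891 594 1484"
- coverage 0.7: "0.7 0.2 891 594 1484"

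The rows just above them differ from each other:

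- coverage 0.5: "0.5 0.3 616 411 1027"
- coverage 0.7: "0.7 0.3 693 462 1154"

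Directly below the table, each site is told to work out its own power or sample size from the parameters it has.

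**The concern.** With precision, significance level and vaccine-type share held fixed, the required number depends on coverage and VE. Two coverages could give the same answer by coincidence, but three identical counts at VE 0.2, after clear differences at every other VE, suggest that one row is wrong.

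At stake is a stated planning figure. Member states are invited to build site protocols from this document, and VE 0.2 lies inside the stated planning range. A site with 50% coverage that reads its target from this row would plan for more patients than the table's own precision criterion needs. It would also conclude that moving from 50% to 70% coverage makes no difference at VE 0.2, which no other pair of rows shows.

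**Working it through.** **Inputs, all from section 4.8 b).** Significance level 0.05, taken as two-sided (z = 1.96). Precision d = 0.2, read as the distance from the VE estimate to its lower limit, which is the upper OR limit minus the OR. Vaccine-type share 0.60, so cases to controls = 0.6/0.4 = 1.5. Coverage among controls p0; OR = 1 − VE.

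**Formula.** The protocol prints none. This one was identified by its fit to the table:

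- p1 = OR·p0 / (1 − p0 + OR·p0)
- cases = 1.96² × [1/(p1(1−p1)) + 1.5/(p0(1−p0))] / [ln(1 + 0.2/OR)]²
- controls = cases/1.5; total = cases/0.6

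**Reproducing the plan's own figures.**

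- Coverage 0.5, VE 0.3: p1 = 0.7/1.7 = 0.4118; bracket = 4.129 + 6 = 10.129; ln(1 + 0.2/0.7) = 0.2513; cases = 3.8415 × 10.129/0.06316 = 616.0. Printed: 616.
- Coverage 0.7, VE 0.2: p1 = 0.56/0.86 = 0.6512; bracket = 4.402 + 7.143 = 11.545; ln(1.25) = 0.22314; cases = 3.8415 × 11.545/0.04979 = 890.7, controls 593.8, total 1,484.5. Printed: 891/594/1,484.

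Over the whole table, 31 of 32 rows agree to within rounding (one patient). Examples of computed against printed totals: 576.5 and 576 (coverage 0.1, VE 0.9); 1,594.7 and 1,595 (0.3, 0.2); 1,154.4 and 1,154 (0.7, 0.3).

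**The disputed row, coverage 0.5 and VE 0.2.** p1 = 0.4/0.9 = 0.4444; bracket = 4.05 + 6 = 10.05; cases = 3.8415 × 10.05/0.04979 = 775.3; controls 516.9; total 1,292.2.

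| | Cases | Controls | Total |
|---|---|---|---|
| Printed | 891 | 594 | 1,484 |
| Computed | 775 | 517 | 1,292 |
| Excess | 116 | 77 | 192 |

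The excess is 192/1,292 = 15%. (116 + 77 = 193; the difference of one is rounding in the printed total.)

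**Precision obtained.** With 891/594, SE = √(4.05/891 + 4/594) = 0.1062, and the upper OR limit is 0.8 × exp(1.96 × 0.1062) = 0.985, which is 0.185 above 0.8. With 775/517, SE = 0.1139 and the upper OR limit is 1.000, a distance of 0.200, the stated target.

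**Checks that need no formula.** Steps in the case count as VE falls from 0.9 to 0.2:

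- coverage 0.3: 63, 84, 103, 122, 141, 160, 180
- coverage 0.7: 51, 72, 94, 119, 144, 170, 198
- coverage 0.5: 48, 65, 84, 101, 121, 139, then 275

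With 775 the last step at coverage 0.5 is 159, in line with the others. Likewise, the excess of cases at coverage 0.7 over coverage 0.5 runs 5, 23, 46, 77 for VE 0.6 to 0.3, then drops to 0 as printed; with 775 it is 116.

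**Other readings of the disputed row (cases).** Symmetric half-width of 0.2 on the OR scale: 630. Full interval width of 0.2: 2,484. Distance of 0.2 to the lower OR limit: 466. 80% power, two-sided: 1,583; with continuity correction: 1,627; one-sided: 1,247. None gives 891.

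**Power.** ln(1.25)/SE is 1.96 with 775/517 and 2.10 with 891/594. Less 1.96, that gives power to detect VE 0.2 of about 50% and about 56%.

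**The case against.** The arithmetic is hard to dispute; the objections go to weight and wording.

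- *It binds nobody.* This is one row of an illustrative grid in a generic protocol. Sites adapt the document, are told to do their own calculation, and need a sample size only where surveillance yields too few cases. No enrolment target or analysis depends on the row. This stands.
- *The error is on the safe side.* A site using the printed row gets better precision than the target, not worse. This stands.
- *The row is marginal.* VE 0.2 is the lowest value in the range. The figures the protocol cites against vaccine-type IPD are 75% for PCV13 and, for PPSV23, an average of 60% with a range of 40% to 70%. At coverage 0.5 every other row is right. This stands. A reader might infer that sites would abandon the analysis because of this row, but that needs a site at 50% coverage, planning on VE 20%, with between 1,292 and 1,484 patients, that makes no calculation of its own. The documents describe no such site.
- *The replacement is not the required sample in every sense.* The row carries a 0.8 power label, and the section mentions both power and precision. At 775/517 power is about 50%, further from 80% than with the printed counts. This stands as a limit on what the corrected figure means. It does not rescue 891, because 80% power would need about 1,583 cases, and the other 31 rows follow the precision criterion alone.
- *The formula is inferred.* True, but the printed row also fails the checks that need no formula.

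**Conclusion.** The coverage 0.5 / VE 0.2 row is wrong as printed. The value consistent with the stated precision and with the rest of the table is 775 cases, 517 controls and 1,292 in total, so the printed row overstates the need by 192 patients, about 15%. It is a minor correction and conservative in direction.

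This rests on a two-sided 5% level, on precision read as the distance to the lower VE limit, and on a formula identified by fit. Two stronger readings should be avoided. One is that the row was demonstrably copied from coverage 0.7: identical counts make that likely, but the documents do not show the cause. The other is that 775/517/1,292 is the required sample outright: it is the size for the precision target only, and the 80% power listed beside it plays no part in the figure.

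**What to change.** Replace the coverage 0.5 / VE 0.2 row with 775 cases, 517 controls and 1,292 total. Add a short note to the table saying that its figures are the sizes that meet the 0.2 precision target and are not derived from the 80% power in the adjoining column. The cost is one table row and one sentence; design, analysis and all other rows stay as they are.
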